5.6 Statistical assumptions and issues

Prior to analysis, statistical assumptions are evaluated for each proposed outcome assessment. The presence of distributional assumptions, influential outliers, and homogeneity of variance, among other common assumptions related to the analyses described here, are assessed. Methods used and results of the assessment of statistical assumptions will be

acknowledged in the final study manuscript(s). In addition, issues related to significant differences between withdrawn, lost to follow-up, and remaining cases as well as changes in study methods over time (e.g. change in study procedures that result in materially different patient outcomes) will be considered. A description of unusual outliers, violated assumptions, or other issues that may impact the integrity of the analyses, and any corrective action (e.g. assumptions evaluated, review of outliers/sensitivity analyses, variable transformations, etc.) will be described in the final study manuscript(s) as applicable.

5.7 Clustered data

Given the small number of participants relative to the number of VA PCPs and facilities nationally, there is little potential for clustering effect among patients receiving care from the same PCPs or at the same VA facility. As a result, provider or facility clustering will not be considered in the final analyses.

5.8 Statistical software

Statistical analysis will be conducted using appropriate and validated software, including SAS, STATA, R, or other comparable statistical programs. The applicable software(s), package(s), and version(s) used for the analyses of study data will be reported in the final manuscript(s).

6.0 Outcome definitions and timing

6.1 Primary outcome (6-month difference in LDL-C)

Baseline (at enrollment) and end-of-study (at 6 months) LDL-C values are defined as the LDL-C measurements obtained from study-related blood draws as processed by the study's centralized laboratory. For participants for whom it is not feasible to visit their local VA facility for a blood draw at baseline, a documented LDL-C value in their medical record may be used for a study measurement, provided it is not older than 6 months from their date of enrollment and a change in lipid-lowering therapy has not occurred between the clinical LDL-C value and study enrollment. For participants for whom it is not feasible to visit their local VA facility for an end-of-study blood draw, a documented LDL-C value in their medical record may be used for a study measurement. The documented LDL-C value closest to the date 6 months after the date of randomization will be used for the end-of-study value. If no 6-month value is available, the study may use an LDL-C value obtained from the medical record during the 6-month observation period, including carry forward of the baseline value.

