4.3.2 End-of-study follow-up and period of observation

Enrolled participants will be observed for a total of 6 months. For the primary (change in LDL-C) and secondary (proportion meeting LDL-C targets) outcomes related to LDL-C, the end-of-study date will correspond to the date 6 months from the date of randomization. The most recent LDL-C value on or after this date, either associated with a completed study-related blood draw or LDL-C value extracted from CDW data (if unable to obtain an end-of-study specimen), will be used as the 6-month LDL-C value.

Similarly, for the secondary outcome associated with intensification of pharmacotherapy, the end-of-study date will correspond to the date 6 months from the date of randomization. All lipid-lowering related prescriptions, either derived from participant survey responses or extracted from CDW data, which are identified as active prior to or after the date of randomization and considered active either on or before the date 6 months from the date of randomization will be considered for analysis. Prescriptions are defined as active if they fall within a time window of one and a half times the total days supply (equivalent to a medication possession ratio of 0.67) from the prescription start date.⁶⁻⁸

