5.5 Missing data

Prior to statistical analysis, outcomes data are reviewed for the amount and pattern of data missingness (*e.g.*, missing at random) using standard statistical software and methods. For outcomes analysis, partially observed outcomes may be imputed using mean or median imputation, multiple imputation, or comparable methods, as appropriate.¹⁶⁻¹⁸ Any necessary imputation will be conducted separately within each treatment arm. Proportions of data missingness, reasons for missingness (if known), and methods used for data imputation if required, including number of imputations and sensitivity analyses performed, will be reported in the final manuscript(s).

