6.2 Secondary outcomes

6.2.1. Proportion meeting LDL-C targets

The proportion of participants meeting individualized clinically significant LDL-C targets (<100mg/dL for primary prevention and <70 mg/dL for secondary prevention) will be determined at 6 months, using the LDL-C values as described for the primary outcome in Section 6.1.

Secondary prevention will be defined as any patient with any of the following:

Pre-existing atherosclerotic disease (ASCVD): acute coronary syndrome in the prior 12 months, history of myocardial infarction, history of ischemic stroke, symptomatic peripheral artery disease including aneurysm, all of atherosclerotic origin.

Presence of any ASCVD risk factors: age ≥ 65 years; prior percutaneous coronary intervention; prior coronary artery bypass graft; other evidence of coronary artery disease; diabetes mellitus; hypertension; chronic kidney disease; current smoking; congestive heart failure; family history of premature ASCVD; elevated coronary artery calcium score, Lp(a), or apoB; or ankle-brachial index < 0.9 .

All other participants will be considered eligible for primary prevention.

The primary or secondary prevention status of each participant will be determined by clinician review of participant medical records through the end-of-study date. The clinician reviewer(s) will be blinded to randomization status. For each participant deemed eligible for secondary prevention, the clinician will record the reason(s) for eligibility in a study database.

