7.2 Primary outcome

The difference in LDL-C reduction after 6 months between the Immediate Results arm and the Delayed Results arm will be assessed. The LDL-C values at baseline and 6 months will first be summarized descriptively for each arm. The change in LDL-C from baseline to 6 months will be calculated for each participant. An independent *t*-test will be employed to compare the mean LDL-C change between the two arms, assuming normally distributed data. If the change scores do not follow a normal distribution, a non-parametric alternative, the Wilcoxon rank-sum test, may be used. The effect size (Cohen's *d*), confidence intervals, and *P* value will be reported to determine the statistical significance of the observed difference. Additionally, potential confounders may be included in regression modeling to ensure the robustness of findings.

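### Section 6.1 lets baseline or early LDL-C values stand in for a missing 6-month value, which can bias the primary estimate and makes its interval too narrow

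*SAP*

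**What the plan says.** SAP section 6.1 defines the 6-month LDL-C in steps. A study blood draw comes first. If that is not feasible, the record value nearest to six months after randomization is used. Failing both, it permits, without requiring, a measurement "obtained from the medical record during the 6-month observation period, including carry forward of the baseline value". No minimum time since randomization is set for such a value, and no limit on how many participants may be filled this way.

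Three other sections bear on the rule:

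- Section 4.3.2 defines the 6-month value differently: "The most recent LDL-C value on or after this date". On that wording a value from before the 6-month date does not qualify.
- Section 5.5 says that "partially observed outcomes may be imputed using mean or median imputation, multiple imputation, or comparable methods, as appropriate". Imputation is to be done separately within each arm, but no method is named as primary.
- Section 6.2.1 determines the LDL-C target outcome "using the LDL-C values as described for the primary outcome in Section 6.1", so the fallback carries over to it.

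The primary test in section 7.2 is an independent t-test to "compare the mean LDL-C change between the two arms, assuming normally distributed data". It makes no distinction between measured and filled values.

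**The concern.** A baseline value carried forward gives a change of exactly zero, whatever happened to the participant. A record value from the first weeks may precede any effect of a therapy change, yet would be labelled a 6-month value. Both then count as full observations in the t-test. For the target outcome, baseline target status can become 6-month target status.

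The SAP is more careful at the other end of the study. Section 6.1 accepts a record value as baseline only if it is at most 6 months old at enrollment and lipid-lowering therapy has not changed since. The end-of-study fallback has neither condition, although therapy escalation is the mechanism behind the sample size in section 3.2. A record baseline carried forward could be about a year old (6 + 6 months) when it serves as the 6-month value.

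At stake are the size of the reported difference and the width of its 95% interval, which sections 5.1 and 5.4 make the reported result. Because 4.3.2, 5.5 and 6.1 give competing rules without an order of precedence, who counts as missing and how the gap is filled are left open.

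**Working it through.** **Inputs.** From section 3.2: change -20% (Immediate) against 0% (Delayed), common SD 30%, 80% power, alpha 0.05, up to 20% loss to follow-up, up to 50% of the Immediate arm without escalation, 122 per arm enrolled. From section 5.1: two-sided test. The percent scale is used because the SAP gives no SD in mg/dL; a carried baseline means zero change on either scale.

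**The SAP's own figure.** Per arm, n = 2(1.96 + 0.8416)² × 30² / 20² = 35.3, so 36 per arm and 72 in total, as stated. The other table rows for change in LDL-C also reproduce (126, 126, 224). Loss to follow-up: 144/0.8 = 180, and 194/0.8 = 242.5, which gives the stated 244 when rounded up to equal arms.

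**Formulas.** Let a share d of an arm with true mean μ be carried forward as zero, with data missing at random:

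- arm mean = (1 - d)μ
- arm variance = (1 - d)·30² + d(1 - d)μ²
- SE = √[(var_I + var_D)/122]
- observed-case SE = 30·√[1/(122(1 - d_I)) + 1/(122(1 - d_D))]
- coverage = Φ(b + 1.96) - Φ(b - 1.96), where b = (true difference - expected difference)/SE

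**Planning case, 20% carried forward in each arm.**

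- Expected difference: 0.8 × (-20) = -16.
- Immediate variance: 0.8 × 900 + 0.16 × 400 = 784. Delayed variance: 720.
- SE = √(1504/122) = 3.51. Observed cases: 30·√(2/97.6) = 4.29.
- Size of b: 4/3.51 = 1.14, so coverage of the true difference is about 79%.
- Interval width (3.92 × SE): 13.8 against 16.8 points.

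A simulation of 10,000 trials agrees: mean difference -15.95, widths 13.8 and 16.9, coverage 79%. Complete data on all 244 would give SE 30·√(2/122) = 3.84, so losing a fifth of the values appears to add precision.

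| True change, Immediate / Delayed | Carried forward, Immediate / Delayed | True difference | Expected difference | SE, filled | SE, observed | Coverage |
|---|---|---|---|---|---|---|
| -20 / 0 | 5% / 5% | -20 | -19.0 | 3.76 | 3.94 | 94% |
| -20 / 0 | 10% / 10% | -20 | -18.0 | 3.68 | 4.05 | 92% |
| -20 / 0 | 20% / 20% | -20 | -16.0 | 3.51 | 4.29 | 79% |
| -10 / 0 | 20% / 20% | -10 | -8.0 | 3.45 | 4.29 | 91% |
| -20 / 0 | 30% / 10% | -20 | -14.0 | 3.53 | 4.33 | 60% |
| -20 / -5 | 0% / 20% | -15 | -16.0 | 3.65 | 4.07 | 94% |

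The -10 row is the average effect if half of the Immediate arm does not escalate (0.5 × -20), with the SD kept at 30%.

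**No true difference.** Both arms fall 10%, with 10% (Immediate) and 30% (Delayed) carried forward. Expected difference: -9 - (-7) = -2. Variances: 819 and 651. SE = √(1470/122) = 3.47. Type I error is about 8.9%.

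**Power with equal 20% missingness.** At -20: 99.5% filled against 99.7% observed. At -10: 64% against 64%.

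**Target outcome.** With 20% of each arm given its baseline status, baseline status balanced and data missing at random, a true 20-point difference becomes 0.8 × 20 = 16.

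Early in-period values give partial attenuation. Its size depends on their timing, which the SAP does not give.

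**The case against.** The strongest reply is that the rule is optional and comes last. A study draw and then a record value near 6 months are tried first, and section 3.4 makes the VA data warehouse and chart review main data sources. Many participants who miss the draw may still have a usable value. The SAP gives no expected carry-forward rate, and at 5% the damage is slight. The 79% also takes the full 20-point effect and missingness at random, meaning that unmeasured participants improved as much as measured ones. All of this stands, and it makes the figures upper bounds. It does not justify keeping the rule in the endpoint definition, since nothing limits its use.

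Four stronger readings are tempting, and the document does not support them:

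- **The bias always runs toward zero.** It does so with equal missingness or no change in the Delayed arm. The -20 / -5 row and the case with no true difference show otherwise, so the rule cannot be defended as conservative either.
- **The trial loses power.** With equal missingness it hardly does.
- **Filled participants escape section 5.5 and missingness will be under-reported.** No precedence between 5.5 and 6.1 is stated, and 5.5 commits to reporting missingness and imputation methods without exempting such values.
- **The fallback sentence contradicts itself, because a baseline value cannot lie within the observation period.** Section 4.3.1 foresees some baseline measurements after randomization, so this is loose wording at most.

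The complete-case population in 4.4.2 requires an end-of-study LDL-C measurement, but replication in it under 7.5 is optional. It is a partial safeguard.

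**Conclusion.** The point holds in a conditional form. Section 6.1 permits filled values to enter the primary and LDL-C target analyses as measured data. The estimated difference shrinks in proportion to the share carried forward when missingness is equal. If the Delayed arm does not change, the shrinkage follows the Immediate arm's share alone. With unequal missingness and a fall in the Delayed arm, the bias can reverse or create a difference. In every scenario the standard error is smaller than the measured data support.

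The size depends on use of the rule: minor at 5% carried forward, material near the 20% loss the SAP plans for, and smaller if the average effect is nearer -10% than -20%. The figures assume missingness at random, SD 30%, 122 per arm and every missing value carried forward. The harm is to the estimate and its interval; with equal missingness the primary test is nearly unaffected. The lack of precedence among 4.3.2, 5.5 and 6.1 does not depend on these assumptions and needs settling in any case.

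**What to change.** 1. State one 6-month measurement window that reconciles sections 4.3.2 and 6.1, and apply it to study draws and record values alike. Removing the fallback sentence alone is not enough, because the nearest-value rule in 6.1 has no limits and would still admit early values.
2. Treat a participant with no LDL-C inside the window as missing for the primary outcome and for 6.2.1.
3. In 5.5, name multiple imputation within arm as the primary method for both LDL-C outcomes, with baseline LDL-C, in-period LDL-C and therapy data as predictors. Early values then inform the imputation without serving as the endpoint. Remove mean and median imputation for these outcomes.
4. Keep baseline carry-forward only as a labelled sensitivity analysis, and report the number of filled participants by arm.

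The cost is SAP wording and modest programming, with no new data. The interval will be wider: in the planning case with 20% missing, about 16.8 points (observed-case approximation) instead of 13.8.

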6.2 Secondary outcomes

6.2.1. Proportion meeting LDL-C targets

The proportion of participants meeting individualized clinically significant LDL-C targets (<100mg/dL for primary prevention and <70 mg/dL for secondary prevention) will be determined at 6 months, using the LDL-C values as described for the primary outcome in Section 6.1.

Secondary prevention will be defined as any patient with any of the following:

Pre-existing atherosclerotic disease (ASCVD): acute coronary syndrome in the prior 12 months, history of myocardial infarction, history of ischemic stroke, symptomatic peripheral artery disease including aneurysm, all of atherosclerotic origin.

Presence of any ASCVD risk factors: age ≥ 65 years; prior percutaneous coronary intervention; prior coronary artery bypass graft; other evidence of coronary artery disease; diabetes mellitus; hypertension; chronic kidney disease; current smoking; congestive heart failure; family history of premature ASCVD; elevated coronary artery calcium score, Lp(a), or apoB; or ankle-brachial index < 0.9 .

All other participants will be considered eligible for primary prevention.

The primary or secondary prevention status of each participant will be determined by clinician review of participant medical records through the end-of-study date. The clinician reviewer(s) will be blinded to randomization status. For each participant deemed eligible for secondary prevention, the clinician will record the reason(s) for eligibility in a study database.

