3.0 Trial Methods

3.1 Trial design

The MVP-ROAR-FH Study is a randomized controlled trial (RCT). MVP participants suspected of carrying a genetic variant associated with familial hypercholesterolemia are recontacted, enrolled, and, upon receipt of a DNA sample, randomly assigned either to an Immediate Results arm, where the return of genetic results intervention occurs at baseline, or a Delayed Results arm, where the intervention is delivered at the end of the study, after 6 months. The intervention consists of variant confirmation testing and reporting, standard genetic counseling, provision of informational resources to the participant and their primary care providers (PCPs), and documentation of the intervention in the medical record.

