3.2 Sample size

The MVP-ROAR-FH Study aims to enroll ten participants into a pilot trial and 244 participants into the RCT.

Sample size is based on the primary outcome of change in LDL-C in each arm after 6 months. Assuming a mean LDL-C reduction of 20% in the Immediate Results arm, a mean LDL-C reduction of 0% in the Delayed Results arm, and a common standard deviation of 30%,² 72 total participants (36 per arm) are needed to have 80% power to detect a significant between-group difference at alpha=0.05. Enrollment of twice this number (144 total) will account for an absence of therapy escalation in up to 50% of participants in the Immediate Results arm. Enrollment of 180 total participants will account for up to 20% loss to follow-up.

| Change in LDL-C at 6 months | | | Total sample size required |
|-----------------------------|-----------------|-----------|----------------------------|
| Immediate Results | Delayed Results | Common SD | |
| -20% | 0% | 30% | 72 |
| -20% | 0% | 40% | 126 |
| -20% | -5% | 30% | 126 |
| -20% | -5% | 40% | 224 |

An important secondary outcome is the proportion of participants in each arm meeting accepted LDL-C targets at 6 months (<100 mg/dL for primary prevention and <70 mg/dL for secondary prevention). In preparatory-to-research analyses, only 175/322 (46%) MVP participants with a potentially pathogenic LDLR variant had a most recent LDL-C <100mg/dL. To have 80% power to detect a between-arm difference of 20% of participants meeting this LDL-C target at alpha=0.05, up to 194 total participants are needed (97 per arm). To account for up to 20% loss to follow-up, a total of 244 participants (122 per arm) are needed.

| Proportion of participants with LDL-C < 100mg/dL at 6 months | | Total sample size required |
|--|-----------------|----------------------------|
| Immediate Results | Delayed Results | |
| 10% | 30% | 124 |
| 20% | 40% | 162 |
| 30% | 50% | 186 |
| 40% | 60% | 194 |

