4.3.1 Baseline assessment

For the purposes of outcomes assessment, baseline is defined as the most recent measurement of a study-related outcome (see Section 6.0) on or prior to a participant's date of randomization, unless otherwise specified. The total number of participants with baseline measurements obtained post-randomization and/or any statistical analysis including a baseline measurement obtained post-randomization will be reported.

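### The LDL-C target each participant must meet (<100 or <70 mg/dL) is set from records through 6 months after randomization, so it can depend on arm; the bias in this secondary outcome is plausible and probably small

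*SAP*

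**What the plan says.** SAP section 6.2.1 compares 6-month LDL-C with <100 mg/dL for participants in primary prevention and <70 mg/dL for those in secondary prevention. On how the class is decided it says: "The primary or secondary prevention status of each participant will be determined by clinician review of participant medical records through the end-of-study date". For the LDL-C outcomes, section 4.3.2 adds that "the end-of-study date will correspond to the date 6 months from the date of randomization".

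Any single item on the section 6.2.1 list puts a participant in secondary prevention. The list has broad items (age 65 or over, hypertension, diabetes, chronic kidney disease, current smoking, known coronary disease). It also has items that depend on a question or a test: "family history of premature ASCVD; elevated coronary artery calcium score, Lp(a), or apoB", and a low ankle-brachial index. The section adds: "The clinician reviewer(s) will be blinded to randomization status". Reasons for secondary-prevention status are recorded; their dates are not mentioned.

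Under section 3.1 the intervention includes genetic counseling, resources for the participant and the primary care provider, and "documentation of the intervention in the medical record". The Immediate Results arm receives this at baseline. The comparator is "a Delayed Results arm, where the intervention is delivered at the end of the study, after 6 months".

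Section 4.3.1 has a baseline rule, but it concerns outcome measurements and applies "on or prior to a participant's date of randomization, unless otherwise specified".

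**The concern.** The target is part of the outcome definition. If it can change after randomization, and the prompts for change reach only one arm during the window, the two arms are not held to one standard. Take two participants with no listed factor charted at randomization and a 6-month LDL-C of 85 mg/dL. The one in the Delayed Results arm counts as a success. The one in the Immediate Results arm counts as a failure if counseling led to a family history of premature disease being written down in the meantime. LDL-C is the same; only the charting differs.

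The effect would enter the arm difference and the relative risk planned in section 7.3.1. Section 3.2 calls this an important secondary outcome and derives the 244 enrollment target from it, whereas the primary outcome needed 180. The primary outcome, change in LDL-C, uses no target and is untouched.

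**Working it through.** **1. Is status fixed at randomization anywhere?** Section 6.2.1 names the end-of-study date, and section 4.3.2 puts that 6 months after randomization. The section 4.3.1 rule covers outcome measurements and gives way where something else is specified, which section 6.2.1 does. The word pre-existing in section 6.2.1 heads only the atherosclerotic disease list; the risk-factor list, which holds the items open to prompting, has no such limit. So status is not fixed at randomization, and no analysis using baseline status is planned.

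**2. The plan's own figure.** For 40% vs 60%, two-sided alpha 0.05 (two-sidedness is stated for the primary test and assumed here), 80% power and the pooled two-proportion formula:

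n = [1.960 × √(2 × 0.5 × 0.5) + 0.8416 × √(0.4 × 0.6 + 0.6 × 0.4)]² / 0.20² = (1.386 + 0.583)² / 0.04 = 96.9, so 97 per arm and 194 in total. Then 97 / 0.80 = 121.25, so 122 per arm and 244 in total. Both match section 3.2.

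Two cautions. The section 3.2 table is headed "Proportion of participants with LDL-C < 100mg/dL at 6 months", a single threshold, so 40% vs 60% is a stand-in for the two-threshold outcome. I also give the higher rate to the Immediate Results arm, as a benefit implies, although the table's columns show the reverse; n is the same either way.

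**3. Size of the bias.** Loss in the Immediate arm's success proportion = s × r × m. All three ranges are assumptions; the SAP gives none of them.

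- s, share in the <100 group at randomization: 10–20%
- r, excess share of these reclassified in the Immediate arm: 10–25%
- m, share of those reclassified with 6-month LDL-C of 70–99 mg/dL: 30–50%

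Results:

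- Minimum: 0.10 × 0.10 × 0.30 = 0.0030, or 0.3 points
- Midpoint: 0.15 × 0.175 × 0.40 = 0.0105, or 1.05 points
- Maximum: 0.20 × 0.25 × 0.50 = 0.0250, or 2.5 points

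At the midpoint 97 × 0.15 × 0.175 = 2.5 participants are reclassified, and 2.5 × 0.40 = 1.0 success becomes a failure. The relative risk goes from 0.60 / 0.40 = 1.50 to 0.5895 / 0.40 = 1.47 (range 1.49 to 1.44).

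**4. Against sampling error.** The standard error of the difference at 97 per arm is √(0.4 × 0.6 / 97 + 0.6 × 0.4 / 97) = 0.070, or about 7 points.

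**5. Effect on the section 3.2 design calculation** (alpha 0.05, 97 per arm, 40% in the Delayed arm):

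- 60.00%: power 80.0%
- 59.70%: 78.8%
- 58.95%: 75.6%
- 57.50%: 68.6%, which needs all three inputs at their maximum

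This is not the power of the planned test. Section 5.4 applies Bonferroni correction to secondary outcomes, and section 6.2 defines two. At alpha 0.025 the midpoint loss takes power from 71.1% to 65.7%.

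**6. Dependence on the assumptions.** With wider ranges (s 10–50%, r 5–30%, m 20–40%) the loss runs from 0.10 × 0.05 × 0.20 = 0.1 points to 0.50 × 0.30 × 0.40 = 6.0 points. A middle case of 25%, 10% and 30% gives 0.75 points. The upper end needs half the participants to have no listed factor at randomization, which is hard to square with so broad a list.

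**The case against.** The strongest defence is that judging 6-month LDL-C against the target that applies at 6 months is a coherent question, and that reading the chart to that date picks up conditions present at randomization but recorded later. That stands, and is why the current rule should be kept as a sensitivity analysis.

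The mechanism is also inferred. Section 3.1 names no calcium scoring, Lp(a), apoB or ankle-brachial testing. Family history is the most plausible route, and it matters only for participants with none of the other factors. The likelier direction is against the intervention, so the bias would not readily create a false positive. Blinded review and recorded reasons are partial safeguards, and section 7.5 permits supplementary analyses. All this limits the weight of the point without answering it: blinding governs the clinicians' judgement, not what is in the chart, and a permitted analysis is not a prespecified one.

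A reader might infer three stronger things that the SAP does not support:

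- That the chart note unblinds the clinicians. The SAP states that they are blinded; how charts are masked is operational detail that the protocol may hold.
- That smoking cessation would move Immediate-arm participants back to the <100 group. Section 6.3.4 measures smoking by survey, status comes from the medical record, and nothing says that quitting reverses a charted entry within the window.
- That the planned test loses power from 80.0% to 75.6%. Those figures belong to the section 3.2 design calculation. They also assume 97 analysed per arm, while the fallback values allowed in section 6.1 could bring the analysed number closer to 122 (88.3% to 84.6% at alpha 0.05).

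**Conclusion.** The point holds in a limited form. By its stated rule, the SAP lets the success criterion of this secondary outcome be set by information arising after randomization, in a window in which only one arm receives the intervention. That arm-dependent charting will occur is plausible but not shown. If it does, it more likely tightens the target in the Immediate Results arm and draws the comparison towards no difference.

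The size is probably small, because age, hypertension, diabetes and smoking already give many participants the <70 target. The estimate of about 1 point of the planned 20 (0.3 to 2.5) rests wholly on assumed inputs and is well below the sampling error of about 7 points. The change is worth making because it is cheap and the outcome set the enrollment target, not because the trial's conclusions are in danger.

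**What to change.** In section 6.2.1, state that for the main analysis prevention status is determined from medical-record entries dated on or before the date of randomization, and that the clinicians record the date of each qualifying reason. Prespecify status through the end-of-study date as a sensitivity analysis, and report the number reclassified after randomization in each arm. Label any power statement for this outcome as the section 3.2 design calculation at alpha 0.05 or as the Bonferroni-corrected test of section 5.4.

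The cost is SAP wording, one added date field (the reasons are already to be recorded) and one extra analysis. The downside is that conditions arising, or first charted, after randomization keep the baseline class in the main analysis, which then concerns the target applicable at randomization; the sensitivity analysis covers the target applicable at 6 months. No clinical target is changed.

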6.2.2. Intensification of pharmacotherapy

The proportion of participants with an intensification of lipid-lowering pharmacotherapy will be determined from baseline and end-of-study prescription data, obtained from the CDW, medical record review, and patient surveys. Intensification of pharmacotherapy at 6-months will be a composite outcome including prescription of new monotherapy, dose escalation of existing pharmacotherapy, or addition of one or more medications to existing pharmacotherapy compared to baseline pharmacotherapy status.

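### The blinding of the clinicians who set prevention status is not secured: the record they read through month 6 documents the intervention in one arm only, unless it is masked

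*SAP*

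**What the plan says.** - **What is judged, and from what.** In SAP 6.2.1 the primary or secondary prevention status of each participant "will be determined by clinician review of participant medical records through the end-of-study date". That status selects the LDL-C target: <100 mg/dL for primary prevention, <70 mg/dL for secondary.
- **The blinding statement.** The same section adds: "The clinician reviewer(s) will be blinded to randomization status". It stands in the paragraph on prevention status and refers to that task.
- **The window.** For the LDL-C outcomes, SAP 4.3.2 says that "the end-of-study date will correspond to the date 6 months from the date of randomization".
- **The intervention.** SAP 3.1 lists "documentation of the intervention in the medical record" among its components. It describes "an Immediate Results arm, where the return of genetic results intervention occurs at baseline" and "a Delayed Results arm, where the intervention is delivered at the end of the study, after 6 months".
- **Intensification.** SAP 6.2.2 takes prescription data "obtained from the CDW, medical record review, and patient surveys". It names no clinician reviewer and makes no statement about blinding.

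**The concern.** A reviewer who opens the chart up to month 6 can expect to find a record of the returned FH result and counseling for an Immediate Results participant, and none for a Delayed Results participant. The chart itself then indicates the arm. The SAP asserts blinding without describing any step that would preserve it.

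This matters for the target outcome because the reviewer's decision sets the threshold against which the same LDL-C value is scored. A participant with LDL-C from 70 to below 100 mg/dL succeeds under primary prevention and fails under secondary prevention. If an FH note prompts a closer search for risk factors in one arm, the outcome definition drifts by arm. SAP 2.0 says that the main manuscript(s) will follow this plan, so the blinding statement would also be carried into the report.

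**Working it through.** **Step 1. Set the timing side by side.**

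| | Immediate Results | Delayed Results | Source |
|---|---|---|---|
| Intervention delivered | baseline | after 6 months | SAP 3.1 |
| Chart documentation is part of it | yes | yes | SAP 3.1 |
| Review window closes | month 6 | month 6 | SAP 6.2.1, 4.3.2 |
| Entry expected inside the window | yes | not yet | follows |

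The asymmetry exists only within the window, because the Delayed arm receives the same documentation later. A review done after that point might find notes in both arms, but the note date, set against the date of enrollment or randomization, would still point to the arm.

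**Step 2. Look for a masking step.** The SAP describes no redaction, no masked abstract and no restriction to records before randomization.

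**Step 3. Ask whether the decision leaves room for judgement.** Many criteria in 6.2.1 are plain chart facts: age, diabetes, hypertension, earlier revascularization, ankle-brachial index. Others need interpretation, such as residual evidence of coronary disease or a family history of early ASCVD. A single criterion is enough for secondary prevention. Judgement can therefore matter only for participants without any clear-cut criterion, and the SAP does not say how many they are.

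**Step 4. Direction.** Over-calling secondary prevention in the Immediate arm imposes the stricter target there and lowers that arm's success rate.

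**Step 5. Scale, on assumptions only.** The plan's own figure comes first. SAP 3.2 gives 97 per arm for 40% versus 60%, two-sided alpha 0.05 (assumed two-sided) and 80% power:

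- n = [1.96 × √(2 × 0.5 × 0.5) + 0.8416 × √(0.4 × 0.6 + 0.6 × 0.4)]² / 0.2² = (1.3859 + 0.5831)² / 0.04 = 96.9, so 97 per arm, 194 in total.
- Allowing for 20% loss: 97 / 0.8 = 121.25, so 122 per arm, 244 in total. Both figures reproduce.

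That calculation is for the <100 mg/dL target alone. I take 60% as the Immediate arm, the direction in which the intervention is meant to work; the table in 3.2 prints the lower proportion under that arm.

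Let x be the extra share of Immediate participants moved to the <70 target, and q the share of those with LDL-C from 70 to below 100. The Immediate proportion falls by x × q. Neither x nor q is in the SAP.

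- x = 0.02, q = 0.20: fall of 0.4 points; power at 97 per arm goes from 80% to 78%.
- x = 0.05, q = 0.30: fall of 1.5 points; power about 74%.
- x = 0.10, q = 0.40: fall of 4.0 points; power 61%.

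These values show only how the mechanism scales. They do not estimate a bias in this trial.

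**The case against.** The strongest defence is that the SAP does state that reviewers are blinded, and the procedure that achieves this may be in the protocol, which is not shown. This stands to the extent that a reader should not infer that blinding fails or that the statement is false. What the SAP supports is narrower: followed as written, its own procedure exposes the arm, so the statement depends on a masking step that the SAP does not give.

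A second defence is that most criteria are objective, one suffices, and the reviewer must record the reason(s) for each secondary-prevention call. This also stands. It limits how many participants could be affected and leaves an audit trail. It does not cover the criteria that need judgement, and it does not make the blinding statement accurate.

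A reader might further infer that intensification would be reported as blinded when it was not. The documents do not support that, because 6.2.2 claims no blinding. Its composite, "prescription of new monotherapy, dose escalation of existing pharmacotherapy, or addition of one or more medications to existing pharmacotherapy", rests mainly on prescription data, and 4.3.2 gives a days-supply rule for when a prescription is active. What remains is a modest gap: record review and surveys are also sources, and no rule says how, or by whom, conflicts between them are settled.

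Nor should a reader assume that any bias favors the intervention. For the target outcome, the over-calling described above works against it.

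**Conclusion.** The point holds for SAP 6.2.1 in limited form. The blinding of prevention-status review is not secured, and 3.1 contradicts it unless the records are masked. The outcome at risk is the proportion meeting LDL-C targets, through the choice of threshold. The LDL-C values themselves come by default from study blood draws processed centrally (6.1) and are not in question here.

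The SAP gives no basis for the size of any shift. The conclusion assumes that the intervention is documented when it is delivered, as 3.1 describes, and that no masking step exists elsewhere. For 6.2.2 there is no false statement to correct, only a safeguard worth adding. The sample size and the primary analysis are unaffected.

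**What to change.** **SAP 6.2.1.** Adopt one of the following:

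1. Determine prevention status only from records dated on or before randomization. Give reviewers a date-limited view or extract, since a live chart would still show later notes. This also stops findings first recorded after randomization from moving the target by arm, which masking alone does not.
2. Keep the window through month 6, but have reviewers score from an extract with FH result and counseling notes removed, prepared under one written rule for both arms by data staff who do not score. Those staff may know the allocation (under 1.3.3 the data manager prepares the randomization tables), which is acceptable because they make no classification.
3. If neither is done, delete or qualify the blinding statement and report the review as unblinded.

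**SAP 6.2.2.** Score intensification by a fixed algorithm from prescription and survey data. Flag conflicts between sources, and have them reviewed only from an extract without study or genetics notes. A baseline cut-off cannot serve here, because the outcome needs records from after randomization.

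**Cost.** SAP wording and the preparation of an extract, including redacted excerpts for free-text items such as family history. Under the cut-off, risk factors first recorded after randomization are lost.
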